8.3 Study Assessments

The following clinical assessments will be used in the study:

- **Palmoplantar Pustulosis Psoriasis Area and Severity Index (ppPASI) (Appendix C):** The ppPASI is the most commonly used disease severity measure use in palmoplantar pustulosis clinic trials. The ppPASI is composed of subscores of erythema (E), pustules/vesicles (P), desquamation/scales (D) on the left (L) and right (R) palm (P) and sole (S) respectively. The PASI produces a numeric score that can range from 0 to 72, with higher PASI scores denoting more severe disease activity. The ppPASI is calculated using following formula:

$$\text{PPPASI} = (E+P+D) \text{ Area} * 0.2 \text{ (RP)} + (E+P+D) \text{ Area} * 0.2 \text{ (LP)} + (E+P+D) \text{ Area} * 0.3 \text{ (RS)} + (E+P+D) \text{ Area} * 0.3 \text{ (LS)}.$$

- **Physician Global Assessment (PGA) (Appendix D):** The physician's global assessment is a widely used outcome measure that relies on physician visual assessment of disease severity. The static PGA determines psoriasis severity at a single point in time, without taking the baseline disease condition into clear (0), almost clear (1), mild (2), moderate (3), severe (4).
- **Dermatology Life Quality Index (DLQI) (Appendix E):** The DLQI is a dermatology-specific quality of life instrument to measure the impact of skin disease on different aspects of health-related quality of life. The questionnaire contains 10 questions, each scored on a 4-point Likert scale.²² The DLQI is calculated by adding the score of each question, resulting in a maximum of 30 and a minimum of 0. The higher the score, the more quality of life is impaired. A score higher than 10 indicates that the patient's life is being severely affected by

their skin disease. The minimal clinically important difference in inflammatory skin disease is a change of 4 points.²³ The DLQI is the most frequently used patient reported outcome measure in randomized controlled trials in dermatology.

- **EuroQol-5D (EQ-5D-5L) (Appendix F):** The EQ-5D is a validated, reliable, and responsive instrument widely used in clinical trials where respondents rate their health in each of 5 dimensions: mobility, self-care, usual activities, pain/discomfort, and anxiety depression.²⁴ This decision results in a 1-digit number that expresses the level selected for that dimension. The digits for the five dimensions can be combined into a 5-digit number that describes the patient's health state. EQ-5D questionnaire also includes a Visual Analog Scale (VAS), by which respondents can report their perceived health status with a grade ranging from 0 (the worst possible health status) to 100 (the best possible health status).
- **Visual Analog Scale, Itch (Appendix G):** The itch visual analogue scale (VAS-itch) is a patient reported pruritis assessment that has been shown to be valid and reliable in the measurement of pruritis and is widely used in dermatology clinical trials.^{25,26} The VAS-itch is a 10 cm line on which patients mark their pruritis intensity on a scale from "no itch" (0 points) to "worst imaginable itch" (10 points).²⁷ The VAS-itch can be interpreted as 0–3 points represents mild pruritis, ≥ 3–7 points moderate pruritis, ≥ 7–9 points severe pruritis, and ≥ 9 points severe pruritis.²⁸
- **Visual Analog Scale, Pain (Appendix H):** The pain visual analogue (VAS-pain) is a patient reported instrument that measures pain intensity. Patients are asked to place a line perpendicular to the VAS line at the point that represents their pain intensity over the past 24 hours. It has been widely used in diverse adult populations, including those with rheumatic diseases.²⁹ The VAS-pain is a continuous 10cm line, anchored by 2 verbal descriptors, one for each symptom extreme. The following cut points on the pain VAS have been recommended to measure postsurgical pain: no pain (0–4 mm), mild pain (5–44 mm), moderate pain (45–74 mm), and severe pain (75– 100 mm).³⁰ In patients with rheumatoid arthritis, the minimal clinically significant change has been estimated as 1.1 points on an 11-point scale (or 11 points on a 100-point scale).³¹
- **(Optional) Photographs:** Standard medical dermatology photographs of the palms and soles will be taken as documented in Appendix B. A training session prior to study initiation to demonstrate proper photographic technique. Detailed instructions on the collection and transmission of digital images will be provided to the Investigator at the time of study initiation.

8.4 Safety Assessments

A complete physical examination, including measuring vital signs and complete blood count, complete metabolic panel, creatine phosphokinase and triglycerides will be performed at baseline, week 16 and EOS. Additionally, patients will be questioned regarding new symptoms at every visit. All safety lab tests will require the subject to be fasting for 8 hours prior to blood collection.

8.5 Subject Withdrawal

Subjects must discontinue deucravacitinib for any of the following reasons:

- Withdrawal of informed consent (a subject's decision to withdraw for any reason)
- Any clinical adverse event, laboratory abnormality, or intercurrent illness which, in the opinion of the investigator, indicates that continued participation in the study is not in the best interest of the subject.
- Noncompliance
- Pregnancy

All subjects who discontinue their participation in the study should comply with protocol-specified early termination procedures as outlined above. The only exception to this requirement is when a subject withdraws consent for all study procedures or loses the ability to consent freely. If a subject withdraws before completing the study, the reason for withdrawal will be documented appropriately.

8.6 Lost to Follow-Up

All reasonable efforts must be made to locate subjects to determine and report their ongoing status. Lost to follow-up is defined by the inability to reach the subject after a minimum of three documented phone calls, faxes, texts, or emails as well as lack of response by subject to one registered mail letter.

8.7 Renumeration

All participants will receive \$90 for each completed study visit.

9 RISKS AND DISCOMFORTS

9.1 Known Drug Side Effects and Toxicities

The understanding of the safety of deucravacitinib is predominantly based on unblinded data from Phase 1 studies, Phase 2 studies in psoriasis and PsA, and Phase 3 studies in psoriasis. In the Phase 1 studies in healthy subjects, DEUC was safe in single doses from 1 to 40 mg and in multiple doses up to 24 mg/day (12 mg BID) for 14 days. Across the studies, the most common event related to deucravacitinib was acneiform rash, which appeared to be dose-related, with the highest incidence at the 12 mg BID dose. These reactions were all mild or moderate, non-serious, managed with topical treatment (when required), reversible, and rarely led to discontinuation of study drug.

In the Phase II clinical trial for patients with psoriasis, there were no significant changes from baseline in mean values of blood counts; serum levels of liver enzymes, lipids, creatinine, or immunoglobulins (IgM, IgA, IgG, and IgE); vital signs; or ECG findings. Cases of asymptomatic increases from baseline in creatine kinase levels were observed in 12 of 44 patients (27%) who received placebo and 57 of 221 (26%) who received deucravacitinib, with no dose dependence and no events resulting in discontinuation of the trial regimen. In participants in the Phase 2 trial who received 12mg daily (n = 44), the dose planned for this protocol, adverse events were reported in 77% of the patients as compared to 51% in the placebo group. Nasopharyngitis (5%), headache (5%), diarrhea (9%), nausea (5%), and upper respiratory tract infection (2%) were the most common adverse events in those treated with deucravacitinib 12mg daily.

Mass General Brigham Institutional Review Board Intervention/Interaction Detailed Protocol

The majority of deucravacitinib clinical data is from an integrated analysis of the completed pivotal Phase III studies (NCT03624127, NCT03611751) and the ongoing long-term extension study (NCT04036435) in psoriasis, which included 1,519 subjects exposed to deucravacitinib. Most of the AEs were mild or moderate in severity and the incidence of SAEs was low. In the 16-week placebo-controlled period the Phase III trials, the incidence of severe AEs and SAEs in the deucravacitinib group was generally similar to the placebo and apremilast groups, and the frequency of AEs leading to treatment discontinuation in the deucravacitinib group was 2.4%, compared to 3.8% for placebo and 5.2% for apremilast.

The proportions of subjects experiencing AEs in the class of “Infections and infestations” and “Skin and subcutaneous tissue disorders” were higher in the deucravacitinib group compared with the placebo and apremilast groups. The most common AEs reported in the deucravacitinib group in the placebo-controlled period were nasopharyngitis (9.0%), upper respiratory tract infection (5.5%), headache (4.5%), diarrhea (4.4%), blood CPK increased (2.7%), and arthralgia (2.3%). Among these AEs, events with a $\geq 1\%$ higher incidence in the deucravacitinib group than placebo were upper respiratory tract infection (5.5% vs 4.1%) and blood CPK increased (2.7% vs 1.2%); none of these AEs was serious.

The reproductive risk potential has not been comprehensively evaluated in humans. DEUC should not be used in pregnant women.

9.2 Other Risks Associated with Study Procedures

Venipuncture: Risks of venipuncture include bruising, pain at site of phlebotomy, fainting, and rarely infection.

9.3 Privacy/Confidentiality Risks

Personal information may be contained in the copies of medical record. This information will be kept confidential by the investigators, and participants will not be identified by name in any publication.

10 BENEFITS

10.1 Known Potential Benefits to Participants

There are currently no FDA approved treatments for PPP and information regarding the efficacy of existing dermatology therapies is limited. JAK-STAT signaling is plays an important role in the activation of many cytokines involved in chronic inflammatory disorders, and therefore, inhibition of this JAK/STAT is an important therapeutic target. Case reports suggest that off-label use of Janus kinase (JAK) inhibitors may be effective in the treatment of PPP. There are reports of successful treatment of PPP, including TNF-induced PPP, with both tofacitinib, an oral JAK1 and JAK3 inhibitor¹⁴⁻¹⁷ and also baricitinib, an oral JAK1 and JAK2 inhibitor.¹⁸

Deucravacitinib is a small molecule that blocks receptor-mediated TYK2, another member of the member of the JAK family.^{32,33} TYK2 regulates the downstream signaling of interleukin (IL)-12, IL-23, and Type I interferon.¹³ Deucravacitinib has previously demonstrated efficacy in phase II and phase III trials of plaque psoriasis. Given that IL-12 and IL-23 are involved in the pathogenesis of both plaque psoriasis

and palmoplantar pustulosis, deucravacitinib is an exciting potential novel therapy for an orphan disease and further investigation is warranted.

10.2 Known Potential Benefits to Society

Some research participants find participating in clinical trials to be a valuable experience, as their participation contributes to an increased understand about potential treatments for a rare disease like PPP.

11 STATISTICAL ANALYSIS

11.1 Data Collection

Protocol-specific case report forms will be developed and completed by the investigators during study visits and then entered into a study-specific RedCap database. REDCap (Research Electronic Data Capture) is a web-based application hosted by Mass General Brigham (MGB) Research Information Science & Computing (RISC), a HIPPA-compliant software application for electronic collection and management of research and clinical study data. Personal identifiers will not be used when collecting and storing data. An enrollment log will be maintained in the regulatory binder/file which is the only location of personal identifiers with unique subject identification number.

11.2 Sample Size

A modified Simon's two-stage design will be used to maximize the safety and efficiency of this clinical trial in an orphan disease.^{34,35} Sample size was calculated based on the primary efficacy endpoint. The null hypothesis that the true rate of ppPASI is 20% will be tested against a one-sided alternative. In the first stage, 8 patients will be accrued. If 2 or fewer patients achieve a ppPASI-50 in these 8 patients, the study will be stopped. Otherwise, 10 additional patients will be accrued for a total of 18. The null hypothesis will be rejected if 7 or more patient achieve a ppPASI-50 in 18 patients. This design yields a type I error rate of 0.05 and power of 0.8 when the true response rate is 50%.

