4.2 Primary Endpoint

- Proportion of participants who achieve at least 50% improvement in the palmoplantar pustular psoriasis area and severity index (ppPASI-50) at 16 weeks.
- **Hypothesis:** 50% of patients treated with deucravacitinib 6 mg once daily for 16 weeks will achieve at least 50% improvement in disease severity (ppPASI-50)

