15 APPENDICES

15.1 Appendix A – Study Scheme

15.2 Appendix B – Study Assessments & Procedures

Visit	1 Screening	2 Baseline	3 Week 4	4 Week 8	5 Week 12	6 Week 16	7 Week 20	8 (EOS) Week 24	Early Termination
Informed consent	X								
Inclusion/exclusion criteria	X								
Medical history	X								
Prior/concurrent medications	X	X	X	X	X	X	X	X	X
New symptoms/side effects		X	X	X	X	X	X	X	X
Dispense study medication		X	X	X	X	X	X		
Assess medication compliance			X	X	X	X	X	X	X
Assessments									
Vital signs		X				X		X	X
Physical exam		X				X		X	X
ppPASI		X	X	X	X	X	X	X	X
PGA		X	X	X	X	X	X	X	X
DLQI		X	X	X	X	X	X	X	X
EQ-5D-5L		X	X	X	X	X	X	X	X
VAS-itch		X	X	X	X	X	X	X	X
VAS-pain		X	X	X	X	X	X	X	X
Photographs (Optional)		X	X	X	X	X	X	X	X
Laboratory Studies									
Urine pregnancy test	X								
CBC, CMP	X					X		X	X
HIV Test	X								
CPK	X					X		X	X
Triglycerides	X					X		X	X
Hep C antibody	X								
Hep B surface antigen	X								
QuantiFERON GOLD TB screen	X								

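### Does 11.2's power of 0.8 fail because the design accrues exactly 8 and 18 patients with no allowance for loss before Week 16?

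*Combined protocol and SAP*

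**What the plan says.** Section 11.2 describes a modified Simon two-stage design. The null is given as "The null hypothesis that the true rate of ppPASI is 20% will be tested against a one-sided alternative". Eight patients enter first, and "If 2 or fewer patients achieve a ppPASI-50 in these 8 patients, the study will be stopped". The text goes on: "Otherwise, 10 additional patients will be accrued for a total of 18". The null is rejected with 7 or more responders among the 18. The operating characteristics are then summarised: "This design yields a type I error rate of 0.05 and power of 0.8 when the true response rate is 50"%.

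Section 4.2 defines the endpoint as a proportion of participants. The hypothesis under it reads: "50% of patients treated with deucravacitinib 6 mg once daily for 16 weeks will achieve at least 50% improvement in disease severity (ppPASI-50").

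The protocol foresees departures. Section 8.5 says "Subjects must discontinue deucravacitinib for any of the following reasons" and lists them, section 8.6 defines loss to follow-up, and the schedule in Appendix B has an "Early Termination" column in which ppPASI is scored. The only discontinuation rate given is in section 9.1, for the 16-week placebo-controlled period of the psoriasis Phase III trials: "the frequency of AEs leading to treatment discontinuation in the deucravacitinib group was 2.4"%.

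The protocol has no dropout allowance, no replacement rule and no rule for a missing Week 16 ppPASI. Section 11.3 refers the reader to a statistical analysis plan for detailed methods; no separate plan is part of the document reviewed.

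**The concern.** The cut-offs apply to the same 8 and 18 patients who are accrued, so nothing separates accrued from evaluable. A patient who leaves before Week 16 stays in the denominator but has no Week 16 score with which to count as a responder. If the 50% in 4.2 is the rate among patients who complete 16 weeks, the rate among those accrued is 50% times the share who reach Week 16, which is below 50% as soon as anyone leaves. The design has almost no margin to absorb this, because its exact power is only just above 0.80.

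The first look is the sensitive point: three responders are needed from eight patients. If early departures make that harder, an effective drug is more likely to be dropped after stage 1. In a rare disease with one small trial, that error is expensive.

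**Working it through.** **Inputs.** Null rate 0.20, alternative 0.50, stop at 2 or fewer of 8, reject at 7 or more of 18 (all section 11.2). Loss of 2.4% is the section 9.1 figure, used as an illustration; 5% and 10% are assumptions.

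**1. The plan's own figure.** With X1 responders among the first 8 and X2 among the next 10,

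P(reject) = Σ over x = 3 to 8 of P(X1 = x) × P(X2 ≥ 7 − x).

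At a rate of 0.50:

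| x | P(X1 = x) | P(X2 ≥ 7 − x) | Product |
|---|---|---|---|
| 3 | 0.2188 | 0.8281 | 0.1812 |
| 4 | 0.2734 | 0.9453 | 0.2585 |
| 5 | 0.2188 | 0.9893 | 0.2164 |
| 6 | 0.1094 | 0.9990 | 0.1093 |
| 7 | 0.0313 | 1 | 0.0313 |
| 8 | 0.0039 | 1 | 0.0039 |

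The sum is 0.8005. The same formula at 0.20 gives 0.0394. Both claims reproduce, reading 0.05 as a ceiling. The chance of stopping at stage 1 when the rate is 0.50 is P(X1 ≤ 2) = 37/256 = 0.1445.

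**2. The least favourable reading.** Suppose the 50% is for completers, every leaver is a non-responder and nobody is replaced. The rate among accrued patients is then 0.50 × (1 − loss):

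| Loss | Rate among accrued | Power | Stop at stage 1 |
|---|---|---|---|
| 0 | 0.500 | 0.8005 | 0.145 |
| 2.4% | 0.488 | 0.775 | 0.161 |
| 5% (assumed) | 0.475 | 0.745 | 0.180 |
| 10% (assumed) | 0.450 | 0.681 | 0.220 |

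With no rate assumed but exactly one patient lost, power is 0.710 if the loss is in the first 8 (stage 1 stop 29/128 = 0.227) and 0.771 if it is in the next 10. At 2.4% the chance of at least one loss is 1 − 0.976^8 = 0.18 in the first 8 and 1 − 0.976^18 = 0.35 in all 18.

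**3. The other reading.** If 50% is the rate among all participants, leavers are already inside it and power is 0.8005 whatever the loss. The implied rate among completers, with leavers as non-responders, is 0.5/0.976 = 51.2%, 0.5/0.95 = 52.6% or 0.5/0.90 = 55.6% for the three losses. At the lower two losses the planning assumption hardly moves.

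**4. Leavers who have a score.** The table in step 2 gives every leaver zero chance of response. If the early-termination ppPASI were used and a share q of leavers met the 50% criterion, the accrued rate would be 0.50 × (1 − loss) + q × loss. With q assumed at 0.25, 10% loss gives 0.45 + 0.025 = 0.475, hence power 0.745 instead of 0.681.

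**5. What a redesign would buy.** Keep 18 patients and the final cut-off of 7, but look at 10 patients and stop at 2 or fewer:

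| | First look at 8 | First look at 10 |
|---|---|---|
| Type I error | 0.0394 | 0.0478 |
| Power, no loss | 0.8005 | 0.864 |
| Power, 5% loss | 0.745 | 0.813 |
| Early stop if true rate 20% | 0.797 | 0.678 |
| Expected N if true rate 20% | 8 + 10 × 0.203 = 10.0 | 10 + 8 × 0.322 = 12.6 |

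To hold 0.80 at 10% loss, one option is to stop at 2 or fewer of 10 and reject at 8 or more of 22 (type I error 0.0492, power 0.807). That needs four more patients if the trial continues, and expected N under 20% is 10 + 12 × 0.322 = 13.9.

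**The case for a change.** The strongest case for a change is that section 4.2 attaches the 50% to patients treated for 16 weeks, which can be read as those who stay, and that the protocol lists several routes out. The 2.4% covers adverse-event stops only; withdrawn consent, noncompliance and loss to follow-up come on top, so total loss could be higher. One departure among the first eight costs nine points of power, and that figure needs no assumed dropout rate. At 10% loss the first look alone limits power to 1 − 0.220 = 0.78, so enlarging stage 2 could not recover 0.80.

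The arithmetic stands, and so does the observation that the protocol does not say how a patient without a Week 16 score counts at either look. What does not stand is the step from there to a wrong power statement. The phrase in 4.2 can equally name the regimen and the time point, and the endpoint just above it is a proportion of participants. Section 11.2 ties its power to a true response rate without mentioning completers. Counting every leaver as a non-responder and replacing nobody are inferences from the fixed counts, not rules in the text. The adverse-event rate also comes from another disease and measures stopping treatment, not a missing score.

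**Conclusion.** No change to the plan is needed. Power of 0.8 at a 50% response rate is correct for the design described (exact 0.8005), and the type I error is 0.0394, below the 0.05 claimed. With the null rate held at 20% of those accrued, losses counted as non-response can only lower that error.

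The possible shortfall depends on reading the 50% as a completer rate, counting all leavers as failures and replacing none. At the one documented rate it is 0.8005 − 0.775 = 0.025, and 0.775 still rounds to the one-decimal figure in 11.2. It becomes material only at assumed losses of 5% or more (0.745, and 0.681 at 10%).

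What is missing is a denominator convention. A sensible analyst would count all dosed patients, treat a missing Week 16 score as non-response and report the number of early leavers beside the result; settling this alters neither the design nor its error control. Moving the first look or adding patients would protect power against loss, but at the cost of weaker early stopping or more patients exposed. The sponsor chose an early look at 8 in an orphan disease for safety and efficiency, and that is a fair balance.

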11.3 Data Analysis

Descriptive statistics will be used to characterize the study population, including demographics, disease characteristics and previous treatments. For the primary outcome, the percentage of participants who achieve a ppPASI-50 response, or at least 50% improvement in ppPASI score, at 16 weeks, the response rate with a 95% CI will be calculated. For all secondary endpoints, summary and descriptive statistics will be used as appropriate, including number of observations, calculation of mean/median, standard deviation range and 95% confidence intervals. The detailed methods are described in the statistical analysis plan.

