	
 ○ Biologics within 12 weeks of baseline visit ○ Systemic steroids, oral immunosuppressants (azathioprine, cyclosporine, methotrexate, mycophenolate mofetil, tacrolimus), oral retinoids (acitretin, isotretinoin), apremilast, or dapsone within 4 weeks of baseline visit ○ Phototherapy within 4 weeks of baseline visit ○ Prescription topical medications (including calcineurin inhibitors, crisaborole, retinoids, steroids, tar, vitamin D analogs) within 2 weeks of baseline visit ● History of active infection and/or febrile illness within 7 days; or infection requiring antibiotic treatment within 30 days; or serious infection requiring hospitalization and/or IV antibiotics within 90 days ● Evidence of other infection including: 
 ○ Active or untreated latent tuberculosis, defined as radiographic or laboratory evidence of active TB or positive quantiferon or PPD, unless the subject has completed the recommended treatment ○ Human immunodeficiency virus infection (positive HIV antibody) ○ Active hepatitis B ○ Active hepatitis C ● Evidence of clinically significant laboratory abnormality including: 
 ○ Absolute WBC count < 3000/mm³ ○ Platelet count < 100,000/mm³ ○ Hemoglobin < 9.0 g/dl ○ ALT or AST > 3 times the upper limit of normal ● History of cancer within the past 5 years, excluding treated non-melanoma skin cancer (basal cell carcinoma, squamous cell carcinoma) ● Other uncontrolled chronic medical condition that may interfere with a patient's ability to participate in the clinical trial ● Major surgery within 4 weeks of baseline visit ● Receipt of live vaccine within 8 weeks of baseline visit ● Pregnant or breastfeeding individuals ● Inability to comply with any of the study procedures ● Individuals who are incarcerated or compulsory detained
Sample Size:	A modified Simon's two-stage design will be used to maximize the safety and efficiency of this clinical trial in an orphan disease. In the first stage, 8 patients will be accrued. If 2 or fewer patients achieve a ppPASI-50 in these 8 patients, the study will be stopped. Otherwise, 10 additional patients will be accrued for a total of 18.

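### Does the unnamed 95% CI for the primary response rate conflict with the one-sided two-stage rule that decides the trial?

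*Combined protocol and SAP*

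**What the plan says.** Section 11.2 sets out the test: "The null hypothesis that the true rate of ppPASI is 20% will be tested against a one-sided alternative". The stages follow: "In the first stage, 8 patients will be accrued", and "If 2 or fewer patients achieve a ppPASI-50 in these 8 patients, the study will be stopped". If the trial continues, 10 more patients bring the total to 18, and the final rule is "The null hypothesis will be rejected if 7 or more patient achieve a ppPASI-50 in 18 patients". The section states a type I error rate of 0.05, and power of 0.8 at a true rate of 50%.

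For the primary outcome, section 11.3 says that "the response rate with a 95% CI will be calculated". The Analysis Plan row of the Protocol Summary says the same. Section 11.3 adds: "The detailed methods are described in the statistical analysis plan". The supplied file has no separate SAP text.

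The Sample Size row of the summary gives the first-stage stop and ends with "Otherwise, 10 additional patients will be accrued for a total of 18". It gives neither the 20% null nor the 7-of-18 cut-off.

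**The concern.** The test and the interval are built differently in two respects. The test allows 5% in one tail, whereas a two-sided 95% CI puts 2.5% in each. The test's error rate also takes credit for the early stop, whereas an ordinary binomial CI treats the 18 patients as a single sample.

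The two can therefore disagree at the boundary. A trial with 7 responders of 18 is positive under 11.2, but it could be published with an interval that includes the null rate. Whether it does depends on the CI method, which the supplied text leaves open and which could in principle be picked after the data are seen. A reader of the summary alone would see the CI as the only inference on the primary outcome. At stake is how a narrowly positive result reads.

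**Working it through.** **Inputs, all from section 11.2.** Null rate 0.20, one-sided; n1 = 8, stop at 2 or fewer; 10 further patients, n = 18; reject at 7 or more; target rate 0.50.

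**1. Reproduce the plan's own figures.** P(reject) = sum over x1 = 3 to 8 of P(X1 = x1) × P(X2 ≥ 7 − x1), with X1 ~ Bin(8, p) and X2 ~ Bin(10, p).

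- At p = 0.50, the terms for x1 = 3 to 8 are 0.1812 + 0.2585 + 0.2164 + 0.1093 + 0.0313 + 0.0039 = 0.8005 (from unrounded terms). The stated power of 0.8 is confirmed.
- At p = 0.20, the terms for x1 = 3 to 6 are 0.0177 + 0.0148 + 0.0057 + 0.0010, with about 0.0001 from the rest, giving 0.0394. This lies within 0.05 read as a ceiling.
- Ignoring the first stage, P(X ≥ 7) for Bin(18, 0.20) is 0.0513 and the power is 0.881. The stated power therefore comes from the two-stage rule.

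**2. 95% CIs at 7/18 (38.9%).**

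- Wald: 0.3889 ± 1.96 × √(0.3889 × 0.6111 / 18) = 0.3889 ± 0.2252.
- Wilson: centre (7 + 1.921) / 21.842 = 0.4084; half-width (1.96 / 21.842) × √(7 × 11 / 18 + 0.960) = 0.2054.
- Exact (Clopper-Pearson): 2.5% point of Beta(7, 12) and 97.5% point of Beta(8, 11).

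| Method | 95% CI at 7/18 | Includes 20%? |
|---|---|---|
| Exact | 17.3% to 64.3% | yes |
| Wald | 16.4% to 61.4% | yes |
| Mid-P | 18.9% to 62.3% | yes |
| Jeffreys | 19.4% to 61.7% | yes |
| Wilson | 20.3% to 61.4% | no |
| Agresti-Coull | 20.2% to 61.5% | no |

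**3. Which cause matters?** Both do. Changing only the level leaves an ordinary exact 90% CI of 19.9% to 60.8%, which still includes 20%. Allowing only for the stages gives a two-stage 95% CI of 18.3% to 67.5%, which also includes it. Doing both gives a two-stage 90% CI of 21.0% to 63.6% at 7/18 and 17.5% to 61.3% at 6/18, in line with the rule.

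**4. How far does the conflict reach?** At 8/18 the exact (21.5% to 69.2%), Wald (21.5% to 67.4%) and Wilson (24.6% to 66.3%) intervals all exclude 20%. At 6/18 the rule does not reject and the Wilson lower limit is 16.3%. Only 7/18 is affected. Its probability is P(reject at 7 or more) minus P(reaching 8 or more after passing stage 1):

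- true rate 20%: 0.0394 − 0.0141 = 0.0253;
- true rate 40%: 0.5332 − 0.3967 = 0.1365, which is 26% of positive trials;
- true rate 50%: 0.8005 − 0.7128 = 0.0876, which is 11% of positive trials.

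**5. Is the ordinary exact 95% CI misleading under two-stage sampling?** Hardly. For true rates from 10% to 90% its coverage under this design is at least 95%, apart from a sliver at about 65.1% to 65.3%, where it falls to 0.937.

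**6. What would the matched interval cost?** The two-stage 90% CI ranks every early stop below every second-stage result, which distorts low second-stage results:

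| Result | Two-stage 90% CI | Ordinary exact 90% CI |
|---|---|---|
| 2/8 (stopped) | 4.6% to 60.0% | 4.6% to 60.0% |
| 3/18 | 11.1% to 60.0% | 4.7% to 37.7% |
| 4/18 | 12.3% to 60.0% | 8.0% to 43.9% |

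Its upper limit hardly moves between 2/8 and 4/18, although 10 more patients have been observed.

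**The case for a change.** The strongest case for a change is that 7/18 is the smallest winning result, where clear reporting counts most. It accounts for 0.0253 of the 0.0394 false-rejection probability, or 64%. The text never says that the rule decides and the interval only describes, and the method is left open. A few sentences would close the gap at almost no cost.

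The arithmetic stands, and so does the observation that the method is unnamed in the supplied text. The rest is weaker. Section 11.2 already says what rejects the null, so a sentence saying that the rule decides would repeat it. Section 11.3 refers its detail to an SAP that is not in the file, so it cannot be shown that the method is open or would be chosen after the data. A summary that omits the null and the final cut-off is abbreviated, and the full rule is in the body. Restating the type I error as at most 0.05 puts into words a ceiling that the design already meets.

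The one substantive proposal, leading with a two-stage 90% CI, gains agreement at 7/18 and pays for it with the distorted intervals at 3/18 and 4/18. An ordinary Wilson 95% CI also agrees with the rule at the boundary: its lower limit is 7.1% at 2/8, 16.3% at 6/18 and 20.3% at 7/18.

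**Conclusion.** The concern is arithmetically right but calls for no change. Followed as written, the plan gives a sound decision: the 7-of-18 rule is explicit, its power is 0.80 and its attained type I error is 0.039, whichever interval is reported. The CI shows how precisely the response rate is estimated. A two-sided 95% CI beside a one-sided 5% test is common practice, and the ordinary exact interval keeps about 95% coverage or better here.

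What remains is an unnamed method, a gap that an analyst would fill sensibly with a standard binomial interval, and a presentational mismatch at one result, with probability 0.025 at a true rate of 20%, 0.14 at 40% and 0.088 at 50%. An analyst reporting 7/18 need only say that the null was tested by the rule in 11.2.

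This rests on three assumptions: that the 95% CI is two-sided, which the text does not say; that all 18 patients are counted when the trial continues; and that no unseen SAP text makes the CI the criterion for success.
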